6.3.3. Onset day

The onset day for an event (e.g. AE, concomitant medication/vaccination) is the number of days between the study intervention and the start date of the event. This is 1 for an event occurring on the same day as a study intervention (and reported as starting after study intervention).

6.3.4. Reporting period of adverse events

Safety data	Collected from	Reporting period for analysis
Solicited events	Chinese participants	Within 7 days following the vaccination, i.e. Day 1-7
Unsolicited solicited events	Chinese participants	Within 30 days following the vaccination, i.e. Day 1-30
SAEs, pIMDs	Chinese participants	6 months after vaccination, i.e. Day 1-183
	Overseas participants	
 Up to study end (Month 6) 6 months after vaccination, i.e. Day 1-183
SAEs related to study intervention, pIMDs related to study intervention, fatal SAEs, AE/SAE leading to withdrawal from study	Chinese participants	
 Up to study end (Month 6 or last ARI visit, whichever is later) 6 months after vaccination, i.e. Day 1-183
	Overseas participants	
 Up to study end (Month 6) 6 months after vaccination, i.e. Day 1-183

Atrial fibrillation (AF) reported as AE or SAE would follow the reporting period of unsolicited AE or SAE, respectively.

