**CONFIDENTIAL**

219815 (RSV OA=ADJ-021)  
Protocol Amendment 1 Final

4. For participants with ARI/complications(s) lasting beyond the ARI closure contact, additional follow-up contacts will be done approximately every 2 weeks (post ARI closure contact) until the resolution of the ARI/complication(s) or study end. These additional follow-up contacts can be done via phone calls.
5. If an ARI is reported during a scheduled surveillance contact, then all the procedures expected at the "participant call" should be performed.
6. Atrial fibrillation (AF) will be considered as adverse events of special interest (AESI) in this study and will be additionally reported in the AF follow-up questionnaire (electronic or paper) in eCRF. The collection of AF will be performed following the AE/SAE reporting periods. The reporting of non-serious AF (Study participants in China only) will be performed according to the unsolicited AE reporting period. The reporting of AF meeting the SAE definition (serious AF) will be performed according to the SAE reporting period.
7. SAEs related to study participation, or to a concurrent GSK medication/vaccine should be collected from the time of consent obtained (prior to vaccination) up to study end.

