**Table 5 Intervals between study visits/contacts for ARI surveillance (Study participants in China only)**

Interval	Length of interval	Allowed interval
Between each surveillance contact (planned or spontaneous report) during the RSV season 	14 days 	±3 days 
Between each surveillance contact (planned or spontaneous report) during the inter-season periods 	30 days 	±5 days 
ARI visit	At 2 days from ARI onset 	2-6 days from ARI onset 
ARI follow-up contact	At 14 days from ARI onset 	14-18 days from ARI onset 
ARI closure contact	At 28 days from ARI onset 	28-35 days from ARI onset 
Between each additional follow-up contact 	At 14 days from last FU contact	±3 days

1. Refer to Section 8.2.2 for details on the surveillance period and methods.

2. Once an ARI event has ended, the scheduled surveillance contacts should resume for that participant. The first surveillance contact should be planned within maximum 14 days after the last ARI follow-up contact during the RSV season and within maximum 30 days after the last ARI follow-up contact during the inter-season periods.

3. For logistical reasons, sites may pre-define the schedule for performing surveillance contacts. In case the site staff reaches the participant outside the schedule, the site may resume to the predefined schedule for the next contact.

4. ARI onset (Day 1) is defined as the first day when the study participant presents at least 2 concomitant ARI symptoms/signs meeting the ARI case definition (see Table 8 in Section 4.2.1).

5. If the ARI event was still ongoing at the first ARI follow-up contact (Day 15), an ARI closure contact should be done approximately 28 days after ARI onset. These contacts can be done via phone calls.

6. Only applicable for participants with ARI/complications(s) lasting beyond the ARI closure contact.

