To evaluate the safety and reactogenicity following the administration of the investigational RSVPreF3 OA vaccine.	
For RSV OA group (China) and Placebo group (China):
 
 
Percentage of participants reporting each solicited administration site event with onset within 7 days after study intervention administration (i.e., the day of study intervention administration and 6 subsequent days).
 
Percentage of participants reporting each solicited systemic event with onset within 7 days after study intervention administration (i.e., the day of study intervention administration and 6 subsequent days).
 
Percentage of participants reporting unsolicited AEs within 30 days after study intervention administration (i.e., the day of study intervention administration and 29 subsequent days).
 
Percentage of participants reporting SAEs after study intervention administration (Day 1) up to 6 months after study intervention.
 
Percentage of participants reporting pIMDs after study intervention administration (Day 1) up to 6 months after study intervention.
 
Percentage of participants reporting SAEs related to study intervention after study intervention administration (Day 1) up to study end.
 
Percentage of participants reporting pIMDs related to study intervention after study intervention administration (Day 1) up to study end.
 
Percentage of participants reporting any fatal SAEs after study intervention administration (Day 1) up to study end.
 
 
For RSV OA group (Overseas):
 
 
Percentage of participants reporting SAEs after study intervention administration (Day 1) up to study end (Month 6).
 
Percentage of participants reporting pIMDs after study intervention administration (Day 1) up to study end (Month 6).
 
Percentage of participants reporting SAEs related to study intervention after study intervention administration (Day 1) up to study end (Month 6).
 
Percentage of participants reporting pIMDs related to study intervention after study intervention administration (Day 1) up to study end (Month 6).
 
Percentage of participants reporting any fatal SAEs after study intervention administration (Day 1) up to study end (Month 6).
 

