AE: Adverse event; ARI: Acute respiratory illness; GMT: Geometric mean titer; LRTD: Lower respiratory tract disease; OA: Older adults; pIMD: potential immune-mediated disease; RSV: Respiratory syncytial virus; SAE: Serious adverse event; SRR: seroresponse rate.

\* Co-primary endpoints, NI criteria are defined in Section 9.1. SRR is defined in Section 9.3.1.

Study end in participants in China: Visit 3 (Month 6) or last ARI visit/contact whichever is later.

Study end in Overseas participants: Visit 3 (Month 6)

\*\*Refer to Section 4.2.1 for case definitions.

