**Table 15**      **Collection and reporting of safety information**

	Screening visit*	Vacc			6 months after vaccination for each participant	Study conclusion***
	Day (-28) to Day 1	D1	D7	D30		
Solicited administration site and systemic AEs (Study participants in China only)						
Unsolicited AEs † (Study participants in China only)						
All SAEs†						
All pIMDs						
SAEs related to study intervention†						
PIMDs related to study intervention						
SAEs related to study participation or concurrent GSK medication/vaccine**						
Fatal SAEs†						
AEs/SAEs leading to withdrawal from the study						
Intercurrent medical conditions						

Vacc: vaccination; D: Day; AE: adverse event; AESI: Adverse event of special interest; SAE: serious adverse event; pIMD: potential immune-mediated disease

Note: Visit 3 (Month 6) is considered at the study conclusion for overseas participants. Visit 3/Month 6 (or last ARI visit/contact whichever is later) is considered as the study conclusion for participants in China. Refer to [Table 1](#) and [Table 3](#) for more details.

\* Applicable for RSV OA Vaccine group (Overseas) study participants only.

\*\* Any SAEs assessed as related to study participation (e.g., protocol-mandated procedures, invasive tests, or change in existing therapy) or related to a GSK product will be recorded from the time a participant consents to participate in the study.

\*\*\*Study conclusion for participants in China is Visit 3 [Month 6] or last ARI visit/contact, whichever is later; and for study participants in Overseas is Visit 3 [Month 6].

† Atrial fibrillation (AF) will be considered as AESI in this study and will be additionally reported in the AF follow-up questionnaire in eCRF. The reporting of non-serious AF (Study participants in China only) will be performed according to the unsolicited AE reporting period. The reporting of AF meeting the SAE definition will be performed according to the SAE reporting period. Fatal AF and Serious AF judged as related to study vaccination will be performed according to the fatal SAE and related SAE reporting period, respectively.

The shaded region in the table indicates time period of data collection.

All SAEs will be recorded and reported to the sponsor or designee immediately and under no circumstance should this exceed 24 hours, as indicated in Section 10.3. The investigator will submit any updated SAE data to the sponsor within 24 hours of it being available.

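### SAP 6.3.4 closes the study-end safety window for participants in China at the last ARI visit, whereas the protocol runs it to the last ARI visit or contact

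*SAP*

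**What the plan says.** Protocol Table 7 makes related SAEs, related pIMDs and fatal SAEs secondary safety endpoints for the two groups in China. For fatal SAEs the endpoint is "Percentage of participants reporting any fatal SAEs after study intervention administration (Day 1) up to study end", and the other two use the same window. The notes to Table 7 define the end point: "Study end in participants in China: Visit 3 (Month 6) or last ARI visit/contact whichever is later". The notes to Table 15 say the same of study conclusion: "Study conclusion for participants in China is Visit 3 [Month 6] or last ARI visit/contact, whichever is later". Table 1 (footnote 8) and Section 4.4 agree.

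SAP 6.3.4 gives the reporting period for these three event types, and for AEs/SAEs leading to withdrawal, as "Up to study end (Month 6 or last ARI visit, whichever is later", with Day 1 to 183 as a second window. SAP 1.1 and 4.3.3.4 refer only to study end without defining it, so 6.3.4 is the one place where the SAP spells it out for these events in China. SAP 4.8 declares a blinded safety analysis and no other departure from the protocol.

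**The concern.** In this protocol an ARI visit and an ARI contact are different events. Table 2 gives them separate columns: one ARI visit for examination and swabbing, then a follow-up contact, a closure contact and additional contacts, all of which can be phone calls. The same table has fatal SAEs, related SAEs and related pIMDs recorded at every one of these later contacts.

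Dropping the contact from the definition therefore removes most of the time by which the study-end window exceeds Visit 3. A programmer who follows 6.3.4 as written would leave out of the study-end tables some events that the protocol has collected and counts in the endpoint. The result would be an undeclared change to protocol-defined secondary safety endpoints.

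**Working it through.** The plan states no figure to reproduce. The check compares the two end dates in days relative to Visit 3, set to 0.

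Inputs:
- Onset *o* ≤ 0, because Protocol 8.2.2.1 says ARI procedures are not done if onset is after Visit 3.
- ARI visit *a*: "2-6 days from ARI onset" (Protocol Table 5).
- Follow-up contact: "14-18 days from ARI onset" (Table 5).
- Closure contact, if the ARI is still ongoing at the follow-up contact: "28-35 days from ARI onset" (Table 5).
- Additional contacts, for illness or complications lasting beyond closure: "additional follow-up contacts will be done approximately every 2 weeks (post ARI closure contact) until the resolution of the ARI/complication(s) or study end" (Table 2, footnote 4). Table 5 allows 14 ± 3 days, that is 11 to 17. One such contact therefore falls 28 + 11 = 39 to 35 + 17 = 52 days from onset.

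Formulas, with *c* the day of the last contact counted from onset:
- SAP end, read literally = max(0, *o* + *a*)
- Protocol end = max(0, *o* + *c*)
- Gap = protocol end − SAP end

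Latest possible SAP end: *o* = 0 and *a* = 6 gives Visit 3 + 6 days.

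Onset on the day of Visit 3 (*o* = 0; SAP end +2 to +6):

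| Last contact | Protocol end | Smallest gap | Largest gap |
|---|---|---|---|
| Follow-up | +14 to +18 | 14 − 6 = 8 | 18 − 2 = 16 |
| Closure | +28 to +35 | 28 − 6 = 22 | 35 − 2 = 33 |
| One additional | +39 to +52 | 39 − 6 = 33 | 52 − 2 = 50 |

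Onset 7 days before Visit 3 (*o* = −7): the ARI visit falls at −5 to −1, so the SAP window ends at Visit 3 itself. The gaps are 14 − 7 = 7 to 18 − 7 = 11 days, 28 − 7 = 21 to 35 − 7 = 28 days, and 39 − 7 = 32 to 52 − 7 = 45 days.

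Earliest onset that can be affected: the gap is positive only if *o* + *c* > 0. With the largest *c* of 18, 35 or 52, that is onset up to 17, 34 or 51 days before Visit 3. An ARI that has already resolved by Visit 3 can therefore still have its follow-up contact afterwards.

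The Day 1 to 183 window does not close the gap. Table 4 puts Visit 3 at least 180 days after Visit 1, that is Day 181 or later, so Day 183 is at most 183 − 181 = 2 days past Visit 3.

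**The case against.** The strongest reply is that the parenthesis is shorthand. The operative words in 6.3.4 refer to study end; SAP 4.7.1 has the final analysis wait for safety data up to study conclusion; and SAP 6.3.2 caps imputed AE end dates at the study conclusion date, which the protocol defines to include the last contact. SAP 4.8 reports no such change, which fits an intention to keep the protocol's meaning. Nothing shows that a shorter window was wanted. This has force on intent, but no SAP text settles the matter, and the only explicit definition is the one that omits contacts.

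A reader might also infer more than the documents support:
- That participants are cut off, or their events lost. They stay in the analysis, their earlier events count, and collection continues at each contact. SAP 4.3.3.4 also lists all SAEs, pIMDs and AEs leading to withdrawal, with no window stated for the listings.
- That deaths from an illness already under way at Month 6 drop out. SAP 6.3.3 counts onset day from the start date of the event. The SAP does not say expressly that window membership follows that date, but if it does, a fatal SAE that began before the cut-off stays inside the window even if death comes later. The exposed events are those that start after the cut-off.
- That the closure-contact gap is typical. Closure contacts are made only if the ARI is still ongoing at the follow-up contact; otherwise the smaller gap applies.

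**Conclusion.** The two documents define study end differently, and the SAP wording, taken literally, truncates the related-SAE, related-pIMD and fatal-SAE endpoints at no later than Visit 3 plus 6 days. For onset on the day of Visit 3 the shortfall is 8 to 16 days with a follow-up contact as the last contact and 22 to 33 days with a closure contact; earlier onsets lose less, and additional contacts add more.

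These figures assume that visits and contacts fall within the Table 5 intervals and that Month 6 in SAP 6.3.4 means Visit 3. What is at risk is a set of descriptive percentages with their confidence intervals. For AEs/SAEs leading to withdrawal, SAP 4.3.3.4 plans a listing only, so no percentage in that section changes. No primary endpoint, hypothesis or power figure is touched. The documents give no way to count the affected events, which are probably few. It is worth correcting because the endpoint is defined by the protocol and the change is undeclared.

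**What to change.** In the SAP 6.3.4 row for participants in China, replace the parenthesis with the protocol's definition: Visit 3 (Month 6) or the last ARI visit or contact, whichever comes later. Derive that date from the study conclusion date already used in SAP 6.3.2, so that one end date serves both the imputation rules and the SAP 4.3.3.4 tables. If the shorter window is intended, declare and justify it in SAP 4.8 instead.

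The cost is one line of the SAP and the matching derivation. No new data are needed, since the protocol already has these events recorded at the later contacts.

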6.3.5. Solicited events

6.3.5.1. Daily recording of solicited events

For studies using paper diaries which have questions in the CRF indicating the presence or absence of solicited events, the following rules are applicable:

- Denominators for the summary of administration site (or systemic) solicited events will be calculated using the number of participants who respond “Yes” or “No” to the question concerning the occurrence of administration site (or systemic) events.
- When a specific solicited event is marked as having not occurred following the study intervention (i.e. SDTM CE.CEOCCUR=N for the specified post-intervention period for the event in question), all daily measurements will be imputed as Grade 0.
- When a specific solicited event is marked as having occurred following the study intervention (i.e. SDTM CE.CEOCCUR=Y for the specified post-intervention period for the event in question), any missing daily recordings will be given imputed values to allow them to contribute to the ‘Any’ rows but not to specific grade rows of the solicited event summary tables.

The following table shows how participants contribute to each category for a specific solicited event over the Day X to Day Y post-intervention period:

Solicited event category	Participants included in the calculation of the numerator
Any	All participants with at least one occurrence of the adverse event at grade 1, grade 2, or grade 3 between Day X and Day Y or with the adverse event marked as present and at least one missing daily recording between Day X and Day Y
Grade 3	All participants with at least one occurrence of the adverse event at grade 3 between Day X and Day Y

6.3.5.2. Duration of events

The duration of an event with a start and end date will be the difference between the start and end date plus one day, i.e., an event that starts on 03MAR2018 and ends on 12MAR2018 has a duration of 10 days.

For solicited administration site and systemic events:

- The duration of a solicited AE with at least one day Grade > 0 is defined as End date(CEENDY) – Start date(CESTDY) + 1, with Start date defined as the first day with the symptom and End date defined as the last day with the symptom in or beyond the solicited period.
- A missing start date will be imputed with the vaccination date.
- For paper diaries, if an ongoing symptom has a missing end date, the end date will be considered equal to vaccination date + 29 days.
- The number of days with grade 3 solicited symptom will be defined considering each day with a known grading=3, irrespective of whether the days are consecutive (if only the max intensity during the ongoing period is recorded and the value is 3, each day of the ongoing period will be counted as grade 3).

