4.3.3.1. Solicited events (Chinese participants only)

- For solicited events during the 7-day follow-up period (i.e., the day of study intervention administration and 6 subsequent days) after vaccination, the following summaries will be provided by group: Compliance in completing solicited events information will be tabulated:
 - Number and percentage of participants with solicited events occurrence status data will be tabulated with exact 95% CI.
- Number and percentage of participants reporting below each individual event will be tabulated with exact 95% CI, for any grade, grade 3 and resulting in medically attended visit:
 - any solicited administration site event
 - any solicited systemic event
 - any solicited event
 - each individual administration site event
 - each individual systemic event
- The percentage of participants with each solicited administration site event and solicited systemic event (any grade and grade 3) will be represented graphically.
- For fever, the number and percentage of participants reporting fever by half degree (°C) cumulative increments during the 7-day follow-up period after vaccination will be tabulated as per GSK grading scale and China grading scale.
- The duration in days of each individual solicited events will be tabulated using descriptive statistics (mean, min, Q1, median, Q3, maximum). The same computations will be done for the number of days with Grade 3 solicited events.

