6.3.2. Handling of Partial Dates

When partially completed dates (i.e., dates missing a day and/or month) are used in calculations, the following standard rules will be applied:

- A missing day will be replaced by 15
- A missing day and month will be replaced by June 30th.

The following exceptions apply:

- Adverse events start dates with missing day:
 - If the month is not the same as the vaccine dose, then the imputed start date will be the 1st of the month.
 - If the event starts in the same month as the vaccine dose, the flag indicating if the event occurred before or after vaccination (AE.AESTRTPT) will be used to complete the date. If ‘after study intervention’ is selected, the imputed start date will match the vaccine dose given during that month. If ‘before vaccination’ is selected, the imputed date will be one day before the vaccine dose given during that month.
- Adverse events start dates with missing day and month:
 - If the year is not the same as the vaccine dose, then the imputed start date will be the 1st of January.
 - If the event starts in the same year as the vaccine dose, the flag indicating if the event occurred before or after vaccination (AE.AESTRTPT) will be used to complete the date. If ‘after study intervention’ is selected, the imputed start date will match the vaccine dose given during that year. If ‘before vaccination’ is selected, the imputed date will be one day before the vaccine dose given during that year.
- Adverse event end dates with missing day: the imputed end date will be the last day of the month or the study conclusion date whichever comes first.
- Adverse event end dates with missing day and month: the imputed end date will be the last day of the year (31st of December) or the study conclusion date whichever comes first.

Incomplete ARI onset/end dates will follow the rules analogous to above.

Incomplete concomitant medication/vaccination start/end dates will follow the rules analogous to above with CM.CMENRTPT status “BEFORE” or “ONGOING” status considered.

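### The imputed end date for an ongoing solicited event (Day 30) is not limited to the participant's time in the study

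*SAP*

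**What the plan says.** SAP 6.3.5.2 defines the duration of an event as "the difference between the start and end date plus one day". For solicited events the end is the last symptomatic day, even if it falls after Day 7: "End date defined as the last day with the symptom in or beyond the solicited period". For paper diaries, "if an ongoing symptom has a missing end date, the end date will be considered equal to vaccination date + 29 days". The rule carries no condition on whether the participant was still in the study.

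The next bullet deals with grade 3 days. Where a maximum intensity of 3 is the only grade recorded for the ongoing period, "each day of the ongoing period will be counted as grade 3".

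SAP 4.3.3.1 tabulates the duration of each solicited event by group (mean, quartiles and extremes) and adds: "The same computations will be done for the number of days with Grade 3 solicited events".

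SAP 6.3.2 handles partially completed dates. For an AE end date with the day missing, "the imputed end date will be the last day of the month or the study conclusion date whichever comes first". If day and month are both missing, the imputed date is the end of the year, again limited by study conclusion. SAP 6.3.5.2 neither repeats this limit nor refers to it.

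**The concern.** A duration summary should not contain days on which the participant was dead or no longer under observation. Protocol 7.2 brings a withdrawn participant's data into the analyses up to withdrawal or last contact. The Day 30 rule adds days beyond that point for anyone who leaves earlier with an open event.

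The SAP already has a convention for this problem in 6.3.2, but 6.3.5.2 does not use it. SAP 6.3.6 stores solicited events that run past the observation period in the AE domain. If the partial-date rule were applied to such an event, a participant with a known end month would be cut at exit, while one with no end date at all would run to Day 30. The record with less information would give the longer event.

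What is at stake is the credibility of the duration and grade 3 day tables. One such participant can set the reported maximum, and the mean of grade 3 days can shift visibly if few participants report a given grade 3 event.

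**Working it through.** **Inputs**

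- Day numbering (SAP 6.3.3): "This is 1 for an event occurring on the same day as a study intervention", so vaccination day is Day 1.
- Duration = end - start + 1 (SAP 6.3.5.2).
- Imputed end = vaccination date + 29 days (SAP 6.3.5.2).
- Solicited period = Days 1-7 (SAP 6.3.4). The ongoing period is taken to start on Day 8.
- L = last day under observation.

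**The SAP's own example.** "an event that starts on 03MAR2018 and ends on 12MAR2018 has a duration of 10 days": 12 - 3 + 1 = 10 days. This reproduces exactly.

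**Day of the imputed end.** 1 + 29 = Day 30.

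**Excess duration.** As written: 30 - start + 1. Limited at exit: L - start + 1. The difference is 30 - L, whatever the start day.

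**Excess grade 3 days from the ongoing period, when a maximum of 3 is all that is recorded.** As written: Days 8-30 = 23. Limited at exit: L - 7. The difference is 23 - (L - 7) = 30 - L.

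| Last day L | Days added after exit (30 - L) | Grade 3 days, as written | Grade 3 days, limited (L - 7) |
|---|---|---|---|
| 8 | 22 | 23 | 1 |
| 10 | 20 | 23 | 3 |
| 14 | 16 | 23 | 7 |
| 20 | 10 | 23 | 13 |
| 29 | 1 | 23 | 22 |

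Example: with onset on Day 2 and exit on Day 10, the duration is 30 - 2 + 1 = 29 days as written and 10 - 2 + 1 = 9 days when limited.

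**Effect on the summaries.** The mean rises by k(30 - L)/n for k affected events among n. The documents give no rate of early exit or of missing end dates, so the following is assumed: every other event lasts 3 days, and affected events start on Day 2 with exit on Day 10.

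| Affected / total | Mean, limited | Mean, as written | Shift |
|---|---|---|---|
| 1 / 700 | 3.01 | 3.04 | 20/700 = 0.03 |
| 1 / 200 | 3.03 | 3.13 | 20/200 = 0.10 |
| 5 / 200 | 3.15 | 3.65 | 100/200 = 0.50 |
| 5 / 50 | 3.60 | 5.60 | 100/50 = 2.00 |

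In every row the maximum goes from 9 to 29 and the median stays at 3. The upper quartile also stays at 3, because even 5 of 50 is 10% of events, short of the top quarter.

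**The case against.** The strongest reply is that the case will seldom arise, and this largely stands.

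- Protocol 7.2 requires participants in China withdrawn because of an AE or SAE to be followed to resolution. Those who leave because of a reaction should therefore have an end date, and the rule would not be invoked.
- Diaries come back at Visit 2 (Protocol Table 1), 30-42 days after vaccination (Table 4). A participant who returns one in the window is past Day 30, so the imputed date lies within follow-up.
- Someone who leaves early may never supply a Yes or No answer and would then be outside the solicited-event denominator (SAP 6.3.5.1).
- Protocol 7.3 requires attempts at contact before a participant is classed as lost.

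The case is not eliminated. Protocol 10.3.5.1 allows solicited events to be reported directly to site staff and has unreturned diaries pursued by telephone. Under 10.3.5.5, nonserious AEs other than AESIs are followed only to study end or loss to follow-up. Death, loss, and withdrawal for a reason other than an AE therefore remain.

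A second reply is that an event open at withdrawal is censored, so ending it at exit understates its duration, while Day 30 is simple and does not shorten the event. For withdrawal this is fair: neither date is known to be right. It does not defend the rule for a death.

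A reader might infer more than the documents support:

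- *A direct contradiction between 6.3.2 and 6.3.5.2.* The first covers partial dates, the second a missing end date of an ongoing solicited symptom. The inputs differ, so the rules are inconsistent in approach only.
- *An inflated upper quartile.* A few affected events would not normally move it, as shown above.
- *A maximum of about 30 grade 3 days.* The ongoing period alone gives at most 23. More requires grade 3 recorded within Days 1-7 as well.
- *A distortion concentrated in the vaccine arm.* This is a plausible expectation if reactions are commoner there, but the documents give no rates, and follow-up to resolution after AE withdrawal works against it.

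**Conclusion.** The point holds as a small gap in a derivation rule. SAP 6.3.5.2 places no limit at exit, and nothing elsewhere in the documents removes the resulting 30 - L days (1 to 22 for exits from Day 29 back to Day 8). For a death the imputed days are plainly wrong; for a withdrawal or loss they are days after last contact about which nothing is known.

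Three conditions must coincide: exit before Day 30, a captured event recorded as ongoing, and no end date. The grade 3 effect needs a fourth, that a maximum of 3 is the only grade recorded for the ongoing period. The 1-to-22 range assumes that the ongoing period begins on Day 8, and the shifts in the mean rest on the stated assumptions about event counts and durations.

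The consequence is confined to the descriptive mean and maximum of duration and grade 3 days in participants in China. Percentages with solicited events and the co-primary analyses are unaffected, and medians would not normally move. This is a desirable correction, not an obstacle to the trial's conclusions.

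**What to change.** Amend SAP 6.3.5.2 so that the missing end date of an ongoing solicited event is the earlier of 29 days after vaccination and the participant's date of death, withdrawal or last contact (study conclusion date). State that the same limit applies when the days of the ongoing period are counted as grade 3. Footnote the duration and grade 3 day tables with the number of imputed end dates per group.

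The change should be in place before the Day 31 analysis, which SAP 4.7.1 treats as final for reactogenicity.

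The cost is one clause, one line of derivation code and a footnote. The downside is that an event still open at withdrawal is cut at exit, so its reported duration is a minimum. SAP 6.3.2 already accepts this for partial AE end dates, and the footnote lets the reader see how many durations are affected.
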